### **Risks:**

The study involves initiating therapy with sildenafil which is already utilized during durable CF pump support in select patients with pulmonary hypertension without any significant known adverse events. A package insert for sildenafil is included in the IRB application. There are the risks associated with phlebotomy which include bruising and discomfort. To ensure confidentiality, all research data will be kept separate from the medical record in locked files with limited access. The 5 min arm ischemia blood pressure cuff method has been well described to assess endothelial function and is not known to be associated with adverse events [32]. In addition, the Endothelix has been cleared by the FDA.

### **Benefits:**

Currently, limited data are available to explain the *in-vivo* mechanisms contributing to thrombosis during CF pump support. In this investigation we hypothesize that free hemoglobin released through hemolysis depletes NO, limits breakdown of pro-thrombotic UL multimers of vWF, and augments platelet function to create a nidus for thrombus formation. The preceding pathway is described in other diseases of ongoing hemolysis and *in-vitro* CF pump studies have also shown greater UL multimers and augmented platelet function triggered by free hemoglobin [10, 11, 25]. Confirmatory *in-vivo* evidence can lead to exploration of several therapeutic agents that may reduce thrombosis. For example, inhaled NO can be given to patients during ECMO support, oral agents that enhance NO signaling such as sildenafil or nitrates can be given to patients with hemolysis on durable CF pump support, and free hemoglobin scavenging agents such as haptoglobin and hemopexin can be infused during ongoing hemolysis [33]. Moreover, as opposed to biological diseases of ongoing hemolysis, the hemolysis stimulus can be removed during CF pump support through device exchange or explantation. In addition to unveiling free hemoglobin induced mechanisms of thrombosis, this proposal will investigate if enhancement of NO signaling can lead to reduced platelet activation and aggregation. In clinical practice we have noted a higher subsequent incidence of pump thrombosis and ischemic stroke in patients with ongoing low-level hemolysis (LDH > 384 U/L) after CF pump implantation which is mitigated inpatients receiving sildenafil for other clinical indications. Further CF LVAD experience with theHeart Mate 3, has also shown that low level hemolysis extends to any abnormal LDH level or can also be evident with haptoglobin level  $\leq$  100 mg/dL. If our hypothesis is confirmed, such patients may benefit from primary thrombosis prevention with augmentation of NO signaling by sildenafil or similar agents, which will be a novel approach to reduce thrombotic events during durable CF pump support.

### **Data Safety Monitoring Plan:**

A data safety monitoring board (DSMB) will be created to review adherence to study protocol and breaks in confidentiality. In addition, any side effects or complications associated with phlebotomy such as bruising or with the initiation of sildenafil therapy including headache, dizziness and hypotension will be carefully tracked. Since sildenafil is typically well tolerated in patients with CF pumps the potential risks are likely minimal. The DSMB will be external and will consist of a heart failure attending cardiologist. [REDACTED]

Adverse event monitoring will be continuously done throughout the study period and a log of any AE's will be kept in an excel file. The DSMB will produce quarterly reports of adverse events that may have occurred during phlebotomy or after administration of drug therapy. To ensure accuracy of data, all adverse events will be verified [REDACTED]. If

greater than or equal to 2 patients experience any significant side effects of phlebotomy or sildenafil therapy, then the protocol will be halted until further notice by the DSMB. These adverse events will be communicated to the IRB by the PI ([name]).

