**Study Population - Inclusion criteria:** Low Level Hemolysis (LLH) is defined as: abnormally elevated LDH  $\geq$  240 U/L, plasma free hemoglobin  $\geq$  10 g/dL, haptoglobin  $\leq$  100 mg/dL. Outpatients  $\geq$  18 years old with ongoing durable CF pump support (HM2 or HM3), off nitrates and sildenafil, will be eligible to participate in this study. If the radial pulse is palpable manually (pulsatile), then those with a systolic blood pressure (BP)  $<$  100 mmHg, taken by a manual blood pressure cuff, will be excluded. If the radial artery pulse is not palpable (non-pulsatile), then those with a Doppler blood pressure  $<$  80 mmHg will be excluded. In non-pulsatile patients, the BP is taken by a Doppler ultrasound at the brachial artery and is closely correlated to the mean arterial BP. Those patients already on sildenafil or nitrates for clinical indications will also be excluded. In addition, patients with an ongoing infection that may predispose to thrombosis will be excluded as will those unwilling or unable to give written, informed consent.

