**Study Protocol:** After obtaining informed consent, baseline demographics and hematologic biomarkers including fasting am PA/A and NO bioavailability measurements (3 tubes [1 tube for platelet aggregometry, 1 tube for exploratory biomarkers including p selectin, CD 40L, GPIIb/IIIa receptor, and 1 tube for NO bioavailability] x 3ml = 9 ml of blood) will be collected. In addition, endothelial function will be assessed by flow mediated dilation of the brachial artery and fingertip temperature changes following a 5 min blood pressure cuff inflation. Patients will be placed, using computerized randomization, into 2 groups to receive the study drug which will be either sildenafil or placebo. More precisely, an enrolled patient will be randomly placed in either the placebo or the sildenafil arm, both of which will be marked as "Study Drug." Neither the patient nor the drug administrator will be aware to which study arm the patient has been designated. Following randomization and if BP is in the acceptable range (see figure 4), 20 mg of the study drug will be administered. Then BP will be recorded every 30 mins for two hours. If BP drop is < 5 mmHg after 2 hours and patient is asymptomatic, they will proceed to take 20 mg of the study drug every 8, starting on day 2 (total 18 doses). Patients will be asked to return to the clinic on day 8 and 20 mg of the study drug will be administered. After 2 hours, which is the time of peak drug concentration, fasting am PA/A and NO bioavailability measurements (3 tubes [1 tube for platelet aggregometry, 1 tube for exploratory biomarkers including p selectin, CD 40L, GPIIb/IIIa receptor, and 1 tube for NO bioavailability] x 3ml = 9 ml of blood) will be collected. In addition, endothelial function will be assessed by flow mediated dilation of the brachial artery and fingertip temperature changes following a 5 min blood pressure cuff inflation. Then the patient will be asked to come back to clinic on the next weekday and if BP is in the acceptable range (see figure 4), 40 mg of the study drug will be administered. If BP remains stable for 2 hours (< 5 mmHg drop and asymptomatic), then patients will continue taking 40 mg every 8 hours. Patients will be asked to return to clinic on day 15. A final 40 mg dose of the study drug will be given and after 2 hours fasting am PA/A and NO bioavailability measurements (3 tubes [1 tube for platelet aggregometry, 1 tube for exploratory biomarkers including p selectin, CD 40L, GPIIb/IIIa receptor, and 1 tube for NO bioavailability] x 3ml = 9 ml of blood) will be collected. In addition, endothelial function will be assessed by flow mediated dilation of the brachial artery and fingertip temperature changes following a 5 min blood pressure cuff inflation. All patients will be on a standard antithrombotic regimen of aspirin 81 mg daily with a target INR of 2-2.5 IU.

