
Endothelial Function Testing will be conducted by non-invasive methodology. As has been previously well described [32], a vascular ultrasound probe will be used to assess the diameter of the brachial artery at the level of the antecubital fossa in the longitudinal view. Then an arm blood pressure cuff will be inflated beyond the systolic pressure for 5 minutes to cause transient ischemia. After deflation of the arm blood pressure cuff, the brachial artery diameter will be recorded again by the ultrasound vascular probe. In addition, by using the noninvasive Endothelix device, we will simultaneously also record figure tip temperature change before and after cuff deflation, as another measure of endothelial function.

Addendum to study protocol:

Aim 2 of this protocol is a randomized, blinded, placebo-controlled study to assess the effect of sildenafil on platelet function in patients supported by left ventricular assist devices. We originally proposed to enroll 46 patients into this study. At this point, 20 participants have successfully completed the study since enrollment which was initiated in 2019. Due to slower than expected enrollment for a variety of reasons, including the COVID-19 pandemic, a competing trial and a reduction in institutional implantation volume of these devices, it is no longer feasible to reach the originally proposed sample size within the planned study period

ending December 30, 2023.

In discussion with my mentoring team, we propose to amend the study protocol to perform an interim analysis at the current sample size of 20 participants. The statistical plan will be carried out as originally proposed in the study plan. If there is a trend at a  $p<0.2$  for a change in platelet function between groups, then we will readjust the required sample size accordingly for the duration of the enrollment period. If this trend is not apparent, then it would be futile to enroll additional patients into this study aim and further enrollment will stop. In this scenario, we will proceed with analysis of proposed study measures with subsequent reporting of findings.

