**Statistical analysis, sample size calculations:** The primary measure of PA/A is the change in ADP-induced AUC assessed by platelet aggregometry, which will be compared between the treatment and placebo groups by an independent samples Student's t test. The null hypothesis is that the mean change in PA/A will be the same in both groups at the 15 day time-point. In a prior single-arm study in patients with ongoing hemolysis from SCA, sildenafil reduced PA/A by around 40% from  $30.6\%\pm15.2$  to  $17.3\%\pm12.4$  [17]. If this is the true population effect with standard deviation of the sildenafil induced change in PA/A among patients on durable CF pump support and if there is no expected change in the placebo group, we would need 23 patients per group (46 total patients) to achieve **85% power** to detect a significant difference in mean reduction with a two-sided alpha of 0.05. Analysis will be by intention-to-treat. Although the primary analysis will be unadjusted, secondary analyses will apply linear regression models to adjust for age, sex, race/ethnicity, duration of device implant, type of device (HM2 or 3) and adherence. Given the small sample, adjustment will be limited to no more than 2 additional variables at a time. If device differences are observed, sub-group analyses by device will be performed. For secondary outcomes, the above analyses will be repeated at 8 days and also comparisons of changes in p-selectin, activated GP IIb/IIIa receptor and platelet cGMP at 8 and 15 days.

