**Plan for recruitment, retention, timeline and check points:** Patients on CF MCS are tracked closely in a centralized electronic medical registry kept by the HF group, which we will continue to leverage as a resource to identify patients. Currently, 52 outpatients identified through our CF MCS patient registry on durable devices with LLH are available for screening and at the current implant rate of 5 durable devices per month, 1 additional patient with LLH becomes available every month. With an estimated 35% ineligibility or withholding consent, 95 patients with LLH will need to be screened to enroll 62 patients. With an additional 25% drop-out rate after enrollment, this will leave 46 patients (23 per group) who will complete the study protocol. Since 52 outpatients with CF pumps and LLH are currently available (which is steady state for our program based on prior 3 years) and taking into account 35% ineligibility or unwillingness to participate at screening, we estimate that 34 patients can be immediately enrolled to get a head start. At the current availability of 1 new LLH patients per month, it will take an additional 42 months to screen and enroll the remaining patients. We will conduct checkpoints every 6 months examining if the anticipated enrollment (table 2) is being achieved. If enrollment is not met by 2 consecutive check points, we may increase recruitment an additional 6-12 months.

**Anticipated results and experimental problems:** We expect that enhancement of NO signaling with Sildenafil in patients with low level hemolysis will lead to a reduction in PA/A. If changes in PA/A are not observed, then exogenous PA/A will be assessed with platelet poor plasma. If PA/A is not affected, then follow-up experiments will have to be designed to identify the LDH and plasma free hemoglobin threshold value at which lower-level hemolysis increases PA/A.

Alternatively, if the expected reduction in PA/A is not observed with sildenafil we may try other pharmacological agents that also enhance NO signaling such as nitrates.

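### Aim 2 adds sildenafil, as an anti-platelet treatment, to aspirin and anticoagulation but does not exclude recent bleeding or plan a bleeding table by arm

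*Combined protocol and SAP*

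**What the plan says.** The Aim 2 title presents sildenafil as an anti-platelet treatment. Aim 2, Study Protocol, puts every patient on aspirin 81 mg daily with a target INR of 2-2.5, and the study drug (sildenafil or placebo) is added to that. The Background lists bleeding with thrombosis among the serious haematological events on these pumps. The section on von Willebrand factor describes an acquired deficiency during pump support and links loss of large multimers to a bleeding tendency.

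- **Eligibility (Aim 2, Study Population).** Entry is limited to adult outpatients. The exclusions are low blood pressure, current sildenafil or nitrates, lack of consent, and infection: "patients with an ongoing infection that may predispose to thrombosis will be excluded". Bleeding is not mentioned.
- **Analysis (Aim 2, Statistical analysis).** The primary comparison is the change in ADP-induced aggregation (PA/A) at day 15. The secondary outcomes are the same analysis at day 8 and "comparisons of changes in p-selectin, activated GP IIb/IIIa receptor and platelet cGMP at 8 and 15 days". The section also states: "Analysis will be by intention-to-treat". It plans no safety comparison.
- **Addendum.** If the look at 20 participants shows no trend, enrolment stops and "we will proceed with analysis of proposed study measures with subsequent reporting of findings".
- **Monitoring (Data Safety Monitoring Plan).** Side effects associated "with the initiation of sildenafil therapy including headache, dizziness and hypotension will be carefully tracked". Any adverse event is logged, and the DSMB reports quarterly on events arising during phlebotomy or after dosing. If at least "2 patients experience any significant side effects of phlebotomy or sildenafil therapy, then the protocol will be halted until further notice by the DSMB".

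**The concern.** If the Aim 2 hypothesis is right, sildenafil reduces platelet aggregation in people who are already on aspirin and an anticoagulant. More bleeding is then the harm to expect from the intended effect. The protocol acknowledges bleeding as a hazard of pump support, but neither the Aim 2 criteria nor the planned comparisons mention it.

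Two things are at stake. The first is patient safety: a patient recently treated for a significant bleed meets the written criteria. The second is interpretation. The Benefits section says that confirming the hypothesis could point towards sildenafil for primary prevention of thrombosis. That argument weighs thrombosis against bleeding, and the plan commits to analysing nothing on the bleeding side.

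**Working it through.** The point rests mainly on the text, so the relevant sections are set side by side. A short calculation then shows what a bleeding table could and could not tell a reader.

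**Step 1. Is bleeding a foreseeable harm on the protocol's own terms?** Yes. The Aim 2 title gives the anti-platelet intent, Study Protocol gives the aspirin and INR background, and the Background names bleeding as serious.

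**Step 2. Could a patient who has bled be enrolled?** None of the listed exclusions covers it. Outpatient status, with ongoing aspirin and anticoagulation, makes an active significant bleed unlikely at entry. It does nothing about a bleed that has resolved and led to discharge. The open case is therefore recent bleeding.

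**Step 3. Would a bleed be recorded and reviewed?** Yes. The log takes any adverse event, and the DSMB reports cover events after dosing whatever their cause. The named drug effects follow the word including, so that list is open. The halt rule covers phlebotomy as well as sildenafil, so a serious puncture-site bleed could count by that route. Bleeding is just not named as a study-drug event.

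**Step 4. Would a bleed be compared by arm?** Nothing in the plan says so. The named outcomes are aggregation, p-selectin, GP IIb/IIIa and cGMP. The phrase proposed study measures in the Addendum refers back to a set that has no bleeding outcome.

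**Step 5. How informative could a table be?** The plan's enrolment figures reproduce: 95 × 0.65 = 61.75, about 62 enrolled, and 62 × 0.75 = 46.5, given as 46 completers. With 1:1 allocation, at most 62 / 2 = 31 patients would receive sildenafil at full enrolment. With zero events in n patients, the one-sided 95% upper limit is 1 − 0.05^(1/n).

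| Patients dosed with sildenafil | Basis | Upper limit with 0 bleeds |
|---|---|---|
| 31 | half of 62, all assumed dosed | 1 − 0.05^(1/31) = 0.092 |
| 13 | assumption: 20 / 0.75 = 26.7 enrolled, about half, all dosed | 1 − 0.05^(1/13) = 0.206 |

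The second row is an illustration. The documents give 20 completers but not the number randomised or dosed. Randomisation precedes dosing, and dosing requires an acceptable blood pressure, so some drop-outs may never have been dosed. Fewer dosed patients would widen both limits.

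**Step 6. Does the fix affect the primary analysis?** No. The test, the alpha and the 23 per group are unchanged.

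**The case against.** The strongest reply is that safety capture already exists. Adverse events are monitored continuously, any event is logged, the DSMB reports quarterly, and logged events can be tabulated by arm after unblinding without a further sentence in the plan. The study is small, each course lasts 15 days, and the patients are outpatients. The step up to 40 mg requires them to be free of symptoms as well as stable in blood pressure. The Risks section says that sildenafil is already used in selected pump patients with pulmonary hypertension. The package insert and consent pages are not visible and may carry bleeding precautions.

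Most of this stands, and it rules out several stronger readings:

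- **That bleeds would go unseen, or could count towards the halt only as sildenafil effects.** The log and DSMB reports do not depend on cause, and the halt rule includes phlebotomy.
- **That attribution of a bleed would be guesswork.** The text says "Neither the patient nor the drug administrator will be aware to which study arm the patient has been designated". It does not say that the DSMB is blinded, it does not state who judges attribution, and part of the verification sentence is redacted.
- **That drop-outs would be missed in a bleeding count.** No section proposes a completers-only safety count. The recruitment section says "With an additional 25% drop-out rate after enrollment, this will leave 46 patients (23 per group) who will complete the study protocol", but that describes the sample size for the platelet outcome.

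The reply does not close two gaps. A log is not an exclusion criterion, and being able to tabulate by arm is not a commitment to do so. Prior use in selected patients with another indication does not remove the need to count the harm implied by the effect under test.

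**Conclusion.** The point holds for eligibility and analysis. Aim 2 does not bar recent clinically significant bleeding, and it plans no comparison of bleeding by arm although it adds an intended platelet inhibitor to aspirin and anticoagulation. On monitoring, the only gap is that bleeding is not named as a study-drug event. The halt rule itself needs no change, because pump patients also bleed without the drug.

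No excess of bleeding can be estimated, since the documents give no rate. The table by arm would be descriptive and could not show safety: zero bleeds among 31 dosed patients would still be compatible with a rate of up to 9%. The primary analysis is unaffected. The exclusion matters only if enrolment continues past the analysis at 20 participants; the table matters either way. The conclusion covers the visible eligibility, analysis and monitoring text, and assumes that the redactions after the DSMB membership and in the verification sentence hide no bleeding rule. The changes should be made because they are cheap and bear on safety.

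**What to change.** 1. **Aim 2, Study Population.** For any enrolment after the analysis at 20 participants, exclude active or recent clinically significant bleeding. An example is a bleed needing transfusion or admission within 30 days; the investigator should set the window.
2. **Aim 2, Statistical analysis.** Add one sentence: bleeding will be tabulated by arm, descriptively and without a test, for every randomised and dosed patient including drop-outs, beside the PA/A result. Take the events from the adverse event log and the medical records, and complete this before unblinding.
3. **Data Safety Monitoring Plan (optional).** Name bleeding as a tracked study-drug event, and notify the DSMB promptly of any bleed after the first dose that needs transfusion or admission. Leave the two-patient halt rule as it is.

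The cost is one exclusion line, one analysis sentence, up to two monitoring sentences and a short record check of the patients already dosed. Eligibility becomes slightly narrower while enrolment is already slow, and with item 3 the DSMB would receive some notices of background bleeds. No visits, assays or extra patients are needed.

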**Alternative Therapies:**

Patients may refuse participation in the study.

**Compensation:**

None. If requested, patients may be reimbursed for transportation.

**Minors as Research:**

It will be ensured that all patients will have been 18 years or older at the time of their enrollment.

